7.2. Study Treatments

Subjects will receive either 1146A formulation (CCI carbomer 980 gel) or placebo. Study medication will be administered via a nasal spray device (1 dose =3 actuations per nostril, each actuation is 140µL). Dosing administration is 3 actuations per nostril per dose, four times a day for 7 days. Subjects will be instructed to alternate nostrils after each actuation.

First administration of study medication will occur at the study site by independent site personnel supervision; first dosing can occur any time prior to 13:00. On Days 2-7, all subjects will administer their initial morning dose immediately following recording of their common cold symptom assessment at 07:00 \pm 2 hours and the remaining 3 doses every 4 hours \pm 30 minutes.

7.2.1. Extent of Exposure

Study medication exposure will be summarized descriptively by treatment group for the Safety population, including the following summaries:

- Number and percentages of subjects who took study medication by study day
- Total number of and percentages of administrations
 - Days 1 to 4
 - For subjects dosing between 8:00-11:00 on Day 1, the target number of medication administration is 96 actuations.
 - For subjects dosing between 11:01-13:00 on Day 1, the target number of medication administration is 90 actuations.
 - Days 1 to 7
 - For subjects dosing between 8:00-11:00 on Day 1, the target number of medication administration is 168 actuations.
 - For subjects dosing between 11:01-13:00 on Day 1, the target number of medication administration is 162 actuations.
- Total dose and average daily dose received
 - Days 1 to 4
 - For subjects dosing between 8:00-11:00 on Day 1, the target number of doses is 13,440 mg and the target average daily dose is 3,360 mg.
 - For subjects dosing between 11:01-13:00 on Day 1, the target number of doses is 12,560 mg and the target average daily dose is 2,520 mg for Day 1 and 3,360 mg for Days 2-4.
 - Days 1 to 7
 - For subjects dosing between 8:00-11:00 on Day 1, the target number of doses is 23,520 mg and the target average daily dose is 3,360 mg.
 - For subjects dosing between 11:01-13:00 on Day 1, the target number of doses is 22,680 mg and the target average daily dose is 2,520 mg for Day 1 and 3,360 mg for Days 2-7.

7.2.2. Treatment Compliance

Treatment compliance is assessed by the recording of dosing times and number of actuations in the subject e-diary. Treatment compliance for Days 1-4 and Days 1-7 will be

summarized descriptively (number of subjects and percentage) for <80% Compliance, 80-120% Compliance, >120% Compliance and by treatment group for the Safety population.

8. Efficacy Analysis

Efficacy analyses will be performed on both the mITT population and PP population. The primary endpoint average nasal symptom score Days 1-4 (ANSS₁₋₄) and secondary efficacy endpoint total symptom score Days 1-4 (ATSS₁₋₄) will be analyzed using the mITT population and PP population, all the other secondary and exploratory efficacy endpoints will be analyzed using the mITT population. The mITT analyses will be considered primary; the PP analyses will be considered supportive of the primary analyses on the mITT population.

8.1. Primary Efficacy Endpoint

The primary efficacy endpoint is average nasal symptom score on Days 1 to 4 (ANSS₁₋₄). At each assessment, the individual nasal symptom scores will be summed to provide the NSS. On each day, the NSS scores at each assessment (excluding the baseline NSS on Day 1) will be averaged (mean) to provide a daily NSS. A subject's ANSS₁₋₄ is calculated as the mean of these daily NSS across study Days 1 to 4.

8.1.1. Primary Analysis

The primary efficacy analysis of the ANSS₁₋₄ in each treatment group will be performed on the mITT population. An analysis of covariance (ANCOVA) at a significance level of 0.05, with factors for treatment, center and Day 1 dosing time stratification, and Baseline NSS (Day 1 prior to the first dose) as a covariate, will be used to test the following hypothesis:

H_0 : ANSS₁₋₄ active group = ANSS₁₋₄ control group

vs.

H_1 : ANSS₁₋₄ active group \neq ANSS₁₋₄ control group

When assumption of normality in ANCOVA model is violated, nonparametric methods, e.g., Wilcoxon rank sum test stratified by center and dosing time strata (i.e., van Elteren test) can be used.

The ANSS₁₋₄ values for each treatment group will be descriptively summarized. For the difference of the ANSS₁₋₄ between the two treatment groups, the mean and the 95%

confidence interval for the mean based on the Wald statistic will also be presented. The two-sided p-value based on the Wald statistic Chi-Square will be calculated.

The descriptive statistics will also be broken down by center, gender, and Day 1 dosing time stratification.

If there are more than 10% of subjects, who are enrolled after Protocol Amendment 3 and in the mITT population, with onset of symptoms of common cold between >48 and ≤ 72 hours from onset date and time and randomization date and time, time of onset of symptoms of common cold will be factored in the analysis of covariance described above for this subset of subjects. The descriptive statistics will also be provided for this subset of subjects.

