3.4. Dose Adjustment/Modifications

No dose modification is permitted in this study.

4. General Statistical Considerations

Continuous data will be summarized by descriptive statistics showing the number of subjects (N), the mean, standard deviation (SD), median and minimum and maximum. Categorical data will be summarized by frequency tables showing the number and percentage of subjects falling into each category. When count data are presented, the percentage will be suppressed when the count is zero in order to draw attention to the non-zero counts. The denominator for all percentages will be the number of subjects in that treatment within the analysis set of interest, unless otherwise specified.

For the summary statistics of all numerical variables unless otherwise specified, minimum and maximum will be displayed to the same level of precision as reported. Mean and median will be displayed to one level of precision greater than the data collected. Standard deviation will be displayed to two levels of precision greater than the data collected. P-values will be rounded to three decimal places. If a p-value is less than 0.001 it will be reported as “<0.001.” If a p-value is greater than 0.999 it will be reported as “>0.999.” Data will be displayed in all listings sorted by treatment group.

Unless otherwise specified, baseline will be defined as the last non-missing evaluation prior to or on the date that the first dose of treatment is taken. The study day will be calculated as assessment date - first dose date of double-blind study drug + 1.

All analyses will be conducted using SAS Version 9.3 or higher.

A two-sided test for primary analysis of the primary efficacy endpoint will be used at a Type I error rate of 0.05 for comparison between active group (i.e., 1146A formulation) and control group. The p-values reported for sensitivity analyses of the primary efficacy

endpoint and statistical analyses of the secondary efficacy endpoints and the exploratory efficacy endpoints will not be adjusted for multiplicity and will be considered nominal.

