4.2. Sample Size

Upon review of the most recent literature (Fazekas et al 2012, Ludwig et al 2013, and Eccles et al 2015), similar studies employing the use of nasal spray products with a similar purported mechanism of action had sample sizes between 153 and 211. Therefore, an approximate sample size of 170 (85 subjects in each treatment group) is considered sufficient for this study.

A sufficient number of subjects will be screened to enroll approximately 170 subjects.

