4.3. Randomization, Stratification, and Blinding

Subjects will be assigned to one of two treatment groups (1146A or placebo) using the method of randomly permuted blocks with a fixed block size in accordance with the stratified randomization schedule. The sites will not receive the randomization schedule, but will be assigned blocks of randomization numbers generated from the IRT system. All site personnel will be blinded to the treatment allocations. GSK and PPD personnel who may influence study outcomes are kept blinded to the treatment allocations.

Subjects who meet all inclusion and exclusion criteria will be randomized to one of the two treatment groups (1146A or placebo) in a 1:1 allocation ratio. The IRT system will randomize and stratify by site and by dosing time on Day 1. The maximum number of subjects each site can randomize will be capped at 26 (15% of the target number of randomised subjects). This is to ensure that the study population is reasonably distributed across as many sites as possible, and not dominated by one or two sites providing the majority of subjects.

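### SAP 8.1.1 takes the ANCOVA confidence interval and p-value from a Wald (chi-square) reference instead of t/F on the residual degrees of freedom, which is very slightly anti-conservative for the primary analysis

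*SAP*

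**What the plan says.** SAP section 4 (General Statistical Considerations) sets the error rate: "A two-sided test for primary analysis of the primary efficacy endpoint will be used at a Type I error rate of 0.05". It treats p-values for the sensitivity, secondary and exploratory analyses as nominal.

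SAP 8.1.1 specifies an ANCOVA in the modified ITT population, "with factors for treatment, center and Day 1 dosing time stratification, and Baseline NSS (Day 1 prior to the first dose) as a covariate". For the treatment difference it then states that the "confidence interval for the mean based on the Wald statistic will also be presented" and that the "two-sided p-value based on the Wald statistic Chi-Square will be calculated". It offers a van Elteren test if normality fails. It names no t or F distribution and no residual degrees of freedom.

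Protocol 9.3.2 names only an analysis of covariance at the 0.05 level, with no Wald or chi-square reference.

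On late onset (more than 48 and up to 72 hours), SAP 8.1.1 says that, above a 10% trigger, "time of onset of symptoms of common cold will be factored in the analysis of covariance described above for this subset of subjects". Protocol 9.3.2 is looser: onset time may be adjusted for in the model, and/or the endpoint may simply be summarized for those subjects.

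**The concern.** In a normal-theory ANCOVA the error variance is estimated from the residuals, so the treatment contrast divided by its standard error follows a t distribution on the residual degrees of freedom; its square follows F. A Wald chi-square on one degree of freedom compares the same ratio with 1.960, as if the variance were known. The error always runs one way: p-values too small, intervals too short.

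What is at stake is the nominal 0.05 of SAP section 4 and the coverage of the reported interval. The discrepancy shrinks as the residual degrees of freedom grow, so it should be slight in the full analysis and larger in any model fitted to a small subset. The method also spreads: SAP 8.2 analyzes the secondary endpoints in the same manner, and SAP 8.1.4 repeats 8.1.1 in the per-protocol population.

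**Working it through.** **Inputs from the documents.** Two-sided alpha 0.05 (SAP section 4). Total n of about 170: "an approximate sample size of 170 (85 subjects in each treatment group) is considered sufficient for this study" (SAP 4.2). Allocation "in a 1:1 allocation ratio" and a cap of 26 subjects per site (SAP 4.3). Model terms as in SAP 8.1.1.

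**Inputs that are assumed.** Neither document gives the number of centers or the size of the late-onset subset. The cap of 26 implies at least 170/26 = 6.5, so 7 centers in the whole trial; the range used is 7 to 30. The trigger is more than 10% of the modified ITT subjects enrolled after Amendment 3. If all 170 counted, that means at least 18 subjects; subset sizes from 18 to 85 are shown. The number of centers represented inside a subset is a separate unknown, taken as 3 to 15 (3 to 10 at n = 18, where degrees of freedom run out).

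**Formulas.** With C centers, the primary model has 1 (intercept) + 1 (treatment) + (C − 1) + 1 (dosing-time stratum) + 1 (baseline) = C + 3 parameters, so df = n − (C + 3). Adding onset time as one term gives df = n − (C + 4). Using the usual residual mean square:

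- true size of the Wald test = P(|t_df| > 1.960)
- shortfall in interval width = 1 − 1.960 / t(0.975, df)

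**Full analysis, n = 170, against the stated 5%.**

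| Centers | df | t(0.975) | True size | Interval too narrow by |
|---|---|---|---|---|
| 7 | 160 | 1.975 | 5.17% | 0.8% |
| 15 | 152 | 1.976 | 5.18% | 0.8% |
| 30 | 137 | 1.977 | 5.20% | 0.9% |

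Protocol 5.8.1 still shows a cap of 45, which would allow 4 centers (170/45 = 3.8). That gives df = 163, 5.17% and 0.7%, so the choice of cap makes no practical difference.

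**Late-onset subset, if fitted as its own model with onset time added and the same Wald reference.**

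| Subset n | Centers in subset | df | True size | Interval too narrow by |
|---|---|---|---|---|
| 18 | 3 to 10 | 11 to 4 | 7.6% to 12.2% | 11% to 29% |
| 34 | 3 to 15 | 27 to 15 | 6.0% to 6.9% | 4.5% to 8% |
| 51 | 3 to 15 | 44 to 32 | 5.6% to 5.9% | 3% to 4% |
| 85 | 3 to 15 | 78 to 66 | about 5.4% | 1.6% to 1.8% |

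**Alternative reading.** If onset time is instead added to the model for all 170 subjects with 7 centers, df = 170 − 11 = 159 and the size is 5.17%, no different from the primary analysis.

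**Check by simulation** (40,000 null data sets per scenario, normal errors). The Wald test rejected in 5.3% at n = 170 with 7 centers and in 8.8% at n = 18 with 7 centers (formula: 9.1%). The t reference held between 4.8% and 5.1% across the scenarios run.

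**The case against.** The best reply is that the primary effect does not matter in practice. A gap of 0.17 to 0.20 percentage points is finer than the normality assumption can support for an average of sums of three 0-to-3 scores, and SAP 8.1.1 itself plans for non-normality. That stands as a statement about size. It does not justify keeping the looser reference when the matching one is free.

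A second reply is that the ANCOVA at 0.05 is the deciding test and the Wald output is supplementary, since it appears with the descriptive summaries and the protocol names only ANCOVA. This is a fair reading, but the Wald p-value and interval are still what the SAP says will be calculated and presented, and no other reference is named for that model. At the least, the text does not say which p-value governs.

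A reader might infer that the late-onset subset is clearly affected, for example a size of 9.1% and an interval 17% too narrow at 18 subjects and 7 centers. The documents do not support that as a finding. It needs a separate subset model, although SAP 8.1.1 is ambiguous and the protocol makes the adjustment optional. It needs the Wald reference to carry over, which follows only by inference from the back-reference to the analysis above. It needs a subset barely over the trigger. And it needs 7 centers within the subset, whereas 7 is a minimum for the whole trial. Section 4 also attaches the 0.05 rate to the primary analysis alone, so no error control is promised for this subset.

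A reader might also suspect a larger primary effect if the Wald statistic used the maximum-likelihood variance (residual sum of squares over n): about 5.9% with 7 centers and 8.1% with 30. The SAP does not name the variance estimator, so this is an open point that clearer wording would close, not something the plan specifies.

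**Conclusion.** The point holds as a minor one. Followed as written, SAP 8.1.1 uses an anti-conservative reference for both the p-value and the interval. For the primary analysis the excess is very small: a true size of 5.17% to 5.20% instead of 5%, assuming n = 170, 7 to 30 centers, normal errors and the usual residual mean square. It could change a conclusion only for a p-value almost exactly at 0.05.

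For the late-onset analysis the effect is conditional and cannot be fixed to one figure, because the model, the reference, the subset size and the center count are all unsettled. It could be material near 18 subjects and is slight by 85. The analysis is supplementary, has no decision rule, and does not bear on the primary decision.

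**What to change.** In SAP 8.1.1, replace both Wald phrases: give the t-based 95% confidence interval for the adjusted mean difference and the ANCOVA F (equivalently t) test, using the residual mean square and the residual degrees of freedom. State that the same applies to the secondary endpoints (SAP 8.2) and the per-protocol analysis (SAP 8.1.4).

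For late onset, choose one of two courses and say so: add onset time to the full modified ITT model with the same t/F reference, or keep the subset descriptive, as protocol 9.3.2 allows. Changing the reference alone would not rescue a subset model with only 4 to 11 residual degrees of freedom, whose estimate would remain hard to interpret.

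The cost is SAP wording, with no change to data collection, the primary model's terms or sample size. P-values become very slightly larger.

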8.1.2. Data Imputation

Dropouts will not be replaced and for the primary analysis, missing data after dropout will not be imputed.

For data that is missing at intermediate assessments from subjects who still continue in the study, the fact that these subjects remain in the study and provide data at subsequent assessments supports the assumption that the mechanism for the missing data at these intermediate assessments is unlikely to be related to either their randomized treatment or the condition under study. Therefore, missing common cold symptom scores between two non-missing symptom scores will be imputed by the mean of the last available and the next available symptom score with the imputed mean rounded up to the next whole number.. Assessment date and time of the imputed common cold symptom scores will not be imputed.

Subjects will be instructed not to take any additional cough/cold medications, including but not limited to, prescription, OTC, non-drug/nutritional supplement, or procedures throughout the study. Subjects will be instructed to use acetaminophen/paracetamol over other OTC medications, but should try to avoid use if possible. In the event that a subject uses any additional cough/cold medication (including acetaminophen/paracetamol), its usage (time and reason for use) will be recorded in the e-diary. The primary analysis (modified ITT) will use the recorded cold symptom scores, irrespective of other cough/cold medication usage. The number of subjects using other cough/cold medications and frequency of use will be summarized by treatment group.

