9.2.5. Handling of Dropouts and Missing Data

Dropouts will not be replaced and for the primary analysis, missing data after dropout will not be imputed.

For data that is missing at intermediate assessments from subjects who still continue in the study, the fact that these subjects remain in the study and provide data at subsequent assessments supports the assumption that the mechanism for the missing data at these intermediate assessments is unlikely to be related to either their randomized treatment or the condition under study. Therefore, missing common cold symptom scores between two non-missing symptom scores will be imputed by the mean of the last available and the next available symptom score.

In the event that more than 10% of subjects do not complete the first 4 days of treatment (i.e. the period over which the primary endpoint is evaluated) or if there is a differential drop-out rate between the treatment groups, sensitivity analyses using

Document Name	CCI	Protocol B_Final_Amendment 4_Clean_QA Review		
Type	Version	Document Identifier	Effective Date	
eido_clinical_doc	1.0; CURRENT; Most-Recent; Effective	090032d580d43d4b	19-May-2017 09:57:58	
Reason For Issue	Auto Issue			

different imputation methods for data that is missing post-discontinuation will be performed. These sensitivity analyses will be detailed in the SAP.

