9.3. Statistical Methods and Analytical Plan

Additional details of the proposed statistical analysis will be documented in the SAP, which will be written following finalization of the protocol and prior to study unblinding.

A review of the study data will be conducted before the study is unblinded, and any decisions made at that meeting leading to changes in the statistical analyses, e.g., additional outcomes and analysis populations, exclusion of subjects or data from analysis, will be documented in the SAP. Any changes in the statistical analysis that must be made after the study is unblinded will be documented separately and described in clinical study report.

Continuous data will be summarized by descriptive statistics showing the number of subjects (N), the mean, standard deviation (SD), median and minimum and

Document Name	CCI	Protocol B_Final_Amendment 4_Clean_QA Review		
Type	Version	Document Identifier	Effective Date	
elido_clinical_doc	1.0; CURRENT; Most-Recent; Effective	090032d580d43d4b	19-May-2017 09:57:58	
Reason For Issue	Auto Issue			

maximum. Categorical data will be summarized by frequency tables showing the number and percentage of subjects falling into each category. All study data will be listed.

Unless stated otherwise, for a parameter the Baseline value is the value of the last valid measurement/assessment prior to the first dose of study treatment.

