4.4.4. Per Protocol (PP) Population

The Per-Protocol (PP) population will be determined from compliance during Days 1 to 4, since this is the period of the primary efficacy evaluation.

Any randomized subjects who violated the following inclusion or exclusion criteria will be reviewed on a case by case basis to determine whether they should be excluded from the PP population.

In addition, any subjects who violated the following criteria will be excluded from the PP population.

- a. Subjects who complete less than 80% or more than 120% of their target number of actuations over Days 1 to 4
- b. Subjects who miss 2 or more doses on any one day during Days 1 to 4
- c. Subjects who miss a total of 4 or more of their doses during Days 1 to 4

- d. Subjects who miss more than 1 nasal assessment on any one day during Days 1 to 4.
- e. Dosing outside of allowable time window (2 or more times on any day during Days 1-4)
- f. Use of prohibited medications during Days 1 to 4 as listed in the protocol
- g. Dosing more than 5 minutes prior to self-assessments of symptoms using the eDiary device at home. This is because dosing time is entered manually and can only allow entrance in the increments of 5 minutes. The manual time to be entered has to be in the past. Since the time for dosing has to be in the past and only in 5 minute increments, subjects may have entered a time for dosing that is earlier than automatic time for symptoms assessments.

Analysis on the PP population will be used as a supplement to the mITT analysis and will be performed for the primary efficacy endpoint average nasal symptom score Days 1-4 (ANSS₁₋₄) and the secondary efficacy endpoint average total symptom score Days 1-4 (ATSS₁₋₄).

5. Subject Disposition

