8.1.3. Sensitivity Analysis for Primary Endpoint

In the event that more than 10% of subjects do not complete the first 4 days of treatment (i.e. the period over which the primary endpoint is evaluated) or if there is a differential drop-out rate between the treatment groups, sensitivity analyses for primary endpoint will be performed using the following methods:

- a. Last observation carried forward (LOCF). If a subject has no further cold assessments after taking an alternative cough/cold medication (including acetaminophen/paracetamol), for subjects in the active group, subsequent symptom scores will be imputed with LOCF+1 (as per the additional sensitivity analysis described below).
- b. Control-based pattern imputation (Ratitch and O'Kelly 2011). The control-based pattern imputation will impute missing scores using available data from placebo subjects for each study day.

Additional sensitivity analyses will be performed whereby cold symptom assessments made within 4 hours after the use of any other cough/cold medication (including acetaminophen/paracetamol) are set to missing and the following imputation algorithm applied:

For subjects in the placebo group, individual symptom scores will be replaced using LOCF; for subjects in the active group, individual symptom scores will be replaced with LOCF+1. If the previous score for an individual symptom is 3 (maximum possible score), then LOCF will be used, as LOCF+1 would result in a value of 4, which is not possible. This imputation algorithm reflects the fact that the true cold symptom score, had alternative medication not been used, would have been at least as severe as the cold symptom score prior to the use of the alternative medication, and it is designed to ensure the imputed values do not introduce a bias in favor of the test product.

The sensitivity analyses will be performed based on the mITT population. Details of sensitivity analyses are provided in Appendix D.

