8.1.4. Secondary Analysis for Primary Endpoint

If more than 20% of the symptom scores in the calculation of the ANSS₁₋₄ for an analysis population are missing, the summaries and analyses described for the ANSS₁₋₄ in Section 8.1.1 will be repeated for that analysis population on the ANSS₁₋₄ calculated without imputation of missing symptom scores (i.e. observed case analysis). The secondary analyses will be performed based on the mITT population.

In addition, the analysis described in Section 8.1.1 will be repeated for the PP population.

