Appendix D – Details of Sensitivity Analyses

[figure not shown]
- A. Sensitivity analysis whereby cold symptom assessments made within 4 hours after the use of any other cough/cold medication (including acetaminophen/paracetamol) will be performed for the primary endpoint ANSS₁₋₄ using last observation carried forward LOCF as follows:
 - a. The nasal symptom scores (blocked nose, runny nose, and sneezing) recorded within 4 hours after the use of any other cough/cold medication (including acetaminophen/paracetamol) are set to missing.
 - b. The missing scores from step a. are imputed,
 - i. for subjects in the Placebo group, using the score from the latest non-missing score before the medication was taken, or
 - ii. for subjects in the Active group, using the score from the latest non-missing score + 1 before the medication was taken if the score is less than or equal 2, or using the score from the latest non-missing score before the medication was taken if the score is equal to 3.
 - c. Missing nasal symptom scores between two non-missing nasal symptom scores are not imputed for this sensitivity analysis.
- B. In the event that more than 10% of subjects do not complete the first 4 days of treatment (i.e. the period over which the primary endpoint is evaluated) or if there is a differential drop-out rate between the treatment groups, sensitivity analyses for the primary endpoint ANSS₁₋₄ will be performed using the following methods:
 1. last observation carried forward (LOCF)
 - a. The missing scores will be imputed using the score of the latest non-missing score before the drop-out.
 - b. If the latest non-missing score before drop-out was made within 4 hours after the use of any other cough/cold medication (including acetaminophen/paracetamol), the score will be set to missing and imputed as described in Section A.

2. Controlled-based pattern imputation.

[figure not shown]
CCI

[figure not shown]
CCI

[figure not shown]
CCI

[figure not shown]
CCI

CCI

CCI

CCI

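### SAP 8.1.2 rounds the imputed mean of two neighbouring symptom scores up to a whole number where Protocol 9.2.5 uses the plain mean; the visible text gives no reason, and no visible planned analysis uses the plain mean

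*SAP*

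**What the plan says.** Protocol 9.2.5 deals with intermittent gaps in subjects who stay in the study. A score missing between two observed scores "will be imputed by the mean of the last available and the next available symptom score". It mentions no rounding.

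SAP 8.1.2 carries over the same rule and the same justification, namely that such gaps are unlikely to be related to treatment or to the condition. It then adds "with the imputed mean rounded up to the next whole number". The justification supports filling gaps by the mean; it does not address rounding. The visible SAP neither explains the addition nor marks it as a change from the protocol. It also does not say whether the rounding applies to each symptom or to the summed NSS.

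The rounded rule feeds the primary analysis. It also feeds the secondary endpoints, which SAP 8.2 analyses in the same manner.

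**The concern.** The two documents give different values for the same missing primary-endpoint score. The SAP's version can only raise a score, never lower it. The endpoint does not need whole numbers: SAP 8.1 sums the symptoms, averages within each day and then averages over days.

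Two things are at stake. First, the mean ANSS and ATSS in each arm are pushed upward by a rule the protocol does not contain, which also affects the relative reduction in the protocol's 17% criterion (Protocol 9.2.3). Second, if gaps or odd-difference neighbours were more frequent in one arm, the treatment difference would move too: against the product if the active arm had more, in its favour if placebo had more.

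**Working it through.** Neither document gives an expected gap rate or a figure for the effect of this rule, so there is no plan figure to reproduce.

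**Inputs from the documents**
- Each symptom is scored 0, 1, 2 or 3 (SAP 3.1).
- NSS is the sum of 3 symptoms (SAP 3.2.1.1); TSS is the sum of 8 (SAP 3.1).
- ANSS1-4 is the mean of four daily means, with the Day 1 baseline excluded (SAP 8.1).
- Post-baseline assessments: 4 per day on Days 2-4. On Day 1 there are 3 in the early stratum (first dose 8:00-11:00) and 2 in the late stratum (11:01-13:00) (SAP 3.1).
- Effectiveness criterion: mean ANSS1-4 at least 17% lower than placebo (Protocol 9.2.3).

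**Assumed, not in the documents**
- Share p of neighbour pairs that differ by an odd number: 20-50%.
- Fraction f of assessments imputed: 5-10%, spread evenly over days.
- Placebo mean ANSS1-4: 3-5.
- Rounding is per symptom, and a mean that is already whole stays unchanged.

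**Step 1: gain per imputed symptom.** For neighbours a and b the gain is ceil((a+b)/2) − (a+b)/2.

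| Neighbours | Mean | Rounded up | Gain |
|---|---|---|---|
| 0, 1 | 0.5 | 1 | 0.5 |
| 1, 2 | 1.5 | 2 | 0.5 |
| 2, 3 | 2.5 | 3 | 0.5 |
| 0, 3 | 1.5 | 2 | 0.5 |
| all others | whole | same | 0 |

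The gain is never negative.

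**Step 2: largest effect of one missed assessment on a subject's ANSS1-4.** With all three nasal symptoms odd, the NSS gains 3 × 0.5 = 1.5.
- Days 2-4: 1.5/4/4 = 0.094
- Day 1, early stratum: 1.5/3/4 = 0.125
- Day 1, late stratum: 1.5/2/4 = 0.188

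If the NSS is rounded instead, the gain is at most 0.5 and these become 0.031, 0.042 and 0.063, one third of the per-symptom values.

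**Step 3: expected rise in an arm mean.** Shift = k × 0.5 × p × f, with k = 3 for ANSS1-4 and k = 8 for ATSS1-4.

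| | f = 5% | f = 10% |
|---|---|---|
| ANSS1-4, p = 20% to 50% | 0.015 to 0.038 | 0.030 to 0.075 |
| ATSS1-4, p = 20% to 50% | 0.04 to 0.10 | 0.08 to 0.20 |

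**Step 4: same f and p in both arms.** The shifts cancel, so the expected absolute difference moves by 0. The relative reduction becomes 0.17 × m/(m + s), with placebo mean m and shift s. At f = 10%:
- m = 3: 0.51/3.030 to 0.51/3.075 = 16.8% to 16.6%
- m = 4: 0.68/4.030 to 0.68/4.075 = 16.9% to 16.7%
- m = 5: 0.85/5.030 to 0.85/5.075 = 16.9% to 16.7%

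**Step 5: illustration of unequal gaps.** With 10% imputed in one arm and 5% in the other, the ANSS1-4 difference moves by 1.5 × p × 0.05 = 0.015 to 0.038. That is 2-6% of 0.68 (17% of a placebo mean of 4), or 2-7% over placebo means 3-5.

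**Step 6: does any planned analysis use the plain mean?**
- Per-protocol: SAP 8.1.4 says "the analysis described in Section 8.1.1 will be repeated for the PP population". Nothing drops the rounding.
- Observed-case (SAP 8.1.4): no imputation at all, and run only if more than 20% of scores are missing.
- Post-medication analysis (SAP Appendix D, A): "Missing nasal symptom scores between two non-missing nasal symptom scores are not imputed for this sensitivity analysis". It runs unconditionally, but it also replaces scores recorded within 4 hours after cough/cold medication.
- LOCF and control-based imputation (SAP 8.1.3): run only if drop-out is above 10% or differs between arms, and aimed at drop-out. The control-based method "will impute missing scores using available data from placebo subjects for each study day"; its detailed steps are redacted and cannot be checked.

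**The case against.** The strongest defence is that this is delegated detail. Protocol 9.3 says: "Additional details of the proposed statistical analysis will be documented in the SAP". A practical purpose is also plausible. The scale is whole-numbered, SAP 8.3.1 tabulates each symptom in frequency tables where 1.5 has no category, and SAP 8.1.3 caps LOCF+1 to keep imputed scores on the scale. The rule is the same in both arms. The 17% criterion is not repeated in the visible SAP, and the dilution in step 4 works against the product.

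Much of this stands. The rounding is an unexplained departure, not a forbidden one. But a need for whole numbers in descriptive tables does not explain rounding in one direction inside an averaged primary endpoint. Nor is a rule applied to both arms conservative by design; where the SAP wants conservatism, it gives the reason and an arm-specific rule (LOCF+1 for active, LOCF for placebo).

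It also stands that the rule is not wholly unchecked. Appendix D analysis A leaves every gap unfilled and so removes the rounding for all subjects. It is a real partial check, though it does not isolate the rounding because it changes post-medication scores as well.

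A reader might infer a larger effect from SAP 4.4.4 item d, which excludes "Subjects who miss more than 1 nasal assessment on any one day during Days 1 to 4" and so seems to allow one gap on each of four days. That would give 1.5 × (1/3 + 3/4)/4 = 0.41 points in the early stratum or 1.5 × (1/2 + 3/4)/4 = 0.47 in the late one. The documents do not support this as a general bound. Item c of the same section excludes subjects who miss 4 or more doses over Days 1-4, and assessments are tied to doses. Four gaps would therefore need at least one dose taken without its assessment, with all three symptoms odd at every gap. Appendix C also classes four or more missed nasal assessments on Days 1-4 as a significant deviation.

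**Conclusion.** The discrepancy is real and minor. Protocol 9.2.5 and SAP 8.1.2 specify different values for the same missing score, the SAP's addition biases both arm means upward, no reason appears in the visible text, and no visible planned analysis uses the plain mean. The word visible matters, because some SAP pages were removed and part of Appendix D is redacted.

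The per-subject maxima in step 2 follow from the scale and the schedule, given per-symptom rounding. The arm-level and relative figures rest on assumed gap rates, odd-pair shares and placebo means.

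A reader might infer that the rounding biases the treatment comparison. The documents do not support that. With equal gap rates and equal odd-pair rates, the absolute ANCOVA difference and the test of equality are not shifted. The SAP assumes gaps are unrelated to treatment, and nothing in the documents points to an imbalance. The 10% versus 5% case is only an illustration.

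**What to change.** Delete the rounding phrase from SAP 8.1.2 and use the unrounded per-symptom mean of the last and next available score, as in Protocol 9.2.5. This also settles whether imputation is per symptom or on the NSS. State that the symptom frequency tables in SAP 8.3.1 use observed scores, and that this does not conflict with the Protocol 9.2.5 sentence applying imputations from Day 1 to Day 8, which closes the paragraph on medication use.

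If the rounding is kept, give the reason in SAP 8.1.2, say whether it applies per symptom or to the NSS, and add one run of the primary ANCOVA with the unrounded mean.

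The cost is one SAP phrase, one line of code and one extra rule for the frequency tables. The change should be made before unblinding, so that it cannot look driven by the results.
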